1.4.1.3 Risk of Pancreatitis, Hepatotoxicity, and Other Gastrointestinal Complications

Eight cases of pancreatitis have been reported to be associated with brentuximab vedotin, including two fatal cases. All cases presented with abdominal pain, nausea, and elevated lipase [72]. One case of acute pancreatitis was also reported in the phase III placebocontrolled trial of brentuximab vedotin consolidation therapy after HSCT for HL [60]. In clinical trials the incidence of acute pancreatitis is $\leq 0.3\%$ and $\leq 0.2\%$ in the postmarketing setting [65].

Hepatotoxicity has been reported in association with brentuximab vedotin, in some cases fatal. The majority of events were mild to moderate asymptomatic transaminase elevations. The reported incidence of hepatobiliary disorder is < 2% in clinical studies and post-marketing experience [65].

Other gastrointestinal complications were reported to be common in trials with brentuximab vedotin, including nausea, vomiting, abdominal pain, and diarrhea, although the majority of these adverse events were Grade 2 or less [54, 56, 58]. Additional serious gastrointestinal complications have been reported, including perforation, hemorrhage, erosion, ulcer, intestinal obstruction, enterocolitis, neutropenic colitis, and ileus.

1.4.1.4 Risk of Infusion Reactions, Pulmonary Toxicity, and Skin and Subcutaneous Tissue Disorders

Two cases of anaphylaxis occurred in phase 1 trials with brentuximab vedotin. Grade 1 or Grade 2 infusion reactions were reported in 12% of participants in the pivotal phase II trials, including chills, nausea, dyspnea, pruritis, fever, and cough [54].

Pulmonary toxicity associated with brentuximab vedotin has been reported, primarily when combined with bleomycin [73]. Pulmonary adverse events were also reported in both the brentuximab vedotin group and the placebo group in a phase III trial of consolidation therapy following ASCT for HL, including two deaths in the brentuximab vedotin group resulting from acute respiratory distress syndrome [60]. Fatal and serious events of non-infectious pulmonary toxicity including pneumonitis, interstitial lung disease, and acute respiratory distress syndrome have been reported with brentuximab vedotin monotherapy. Although a causal relationship has not been established, pulmonary toxicity related to brentuximab vedotin monotherapy has not been ruled out [65].

Although rare, fatal and serious Stevens-Johnson syndrome and toxic epidermal necrolysis have been reported in association with brentuximab vedotin [54, 65, 74]. Rash and alopecia were common adverse events reported in the pivotal phase II clinical trials [54, 56, 58].

1.4.1.5 Risk of Embryo and Fetal Harm and Impaired Fertility

Decreased embryo viability and teratogenicity, including fetal malformations, have been described in animal studies. Brentuximab vedotin may damage spermatozoa and testicular tissue, resulting in possible genetic abnormalities. Hence women receiving

brentuximab vedotin and female partners of men receiving brentuximab vedotin should take measures to prevent pregnancy during treatment with brentuximab vedotin and for at least six months after the final dose of brentuximab vedotin. Requirements for contraception are outlined in protocol section 5.3.1.2. Decreased male fertility has also been associated with brentuximab vedotin in animal studies [54, 55, 65].

1.4.1.6 Risk of Drug Interaction with Cytochrome P450 3A4 Inhibitors or Inducers, or P-glycoprotein Inhibitors

Concomitant use of strong Cytochrome P450 3A4 (CYP3A4) inhibitors or inducers, or P-glycoprotein (P-gp) inhibitors, has the potential to affect the exposure to MMAE. Participants who are receiving strong CYP3A4 inhibitors or inducers, or P-gp inhibitors, should be closely monitored for adverse reactions [55]. A specific precaution for potential drug interactions is provided in Section 5.3.4.1, and examples are provided in Appendix 3. These agents will be avoided whenever possible.

1.4.2 Benefits

As noted in section 1.1, there are no FDA-approved therapies for dcSSc, and immunosuppressive drugs do not adequately control disease [6]. Although individual participants in this trial should not anticipate direct benefit, a dose escalation safety study is the first step in evaluating brentuximab vedotin as a treatment for dcSSc. A future placebo-controlled clinical trial testing the efficacy of brentuximab vedotin for dcSSc could then lead to benefit for individuals suffering from this morbid and life-threatening condition.

2. OBJECTIVES

2.1 PRIMARY OBJECTIVE

To assess the safety and tolerability of brentuximab vedotin in diffuse cutaneous systemic sclerosis (dcSSc).

2.2 SECONDARY OBJECTIVES

Safety Objectives

- 1. To assess safety events that occur during and following brentuximab vedotin administration in deSSc.
- 2. To assess peripheral neuropathy and neutropenia during and following brentuximab vedotin administration in dcSSc.

Exploratory Efficacy Objectives

- 1. To assess cutaneous, pulmonary, and other clinical manifestations of dcSSc during and following brentuximab vedotin administration.
- 2. To assess patient-reported quality of life measures in dcSSc during and following brentuximab vedotin administration.

2.3 EXPLORATORY MECHANISTIC OBJECTIVES

- 1. To analyze immune cell populations and cytokines in the skin and blood during and following brentuximab vedotin administration.
- 2. To analyze autoantibodies and soluble CD30 during and following brentuximab vedotin administration.
- 3. To analyze genetic signatures of disease, inflammation, and fibrosis during and following brentuximab vedotin administration.

3. STUDY DESIGN

3.1 DESCRIPTION

This trial will be conducted as a multicenter prospective double blind placebo-controlled dose escalation safety study with brentuximab vedotin and stable background immunosuppressive therapy in adult individuals with dcSSc. Adult male and female participants with dcSSc will be recruited by a collaborative group of clinical sites in the United States. Participants who meet the eligibility criteria will be enrolled without regard to gender, race, or ethnicity. Eligible participants will be randomly assigned to study treatment, either brentuximab vedotin or placebo equivalent in a 6:2 ratio favoring brentuximab vedotin. Three dose cohorts are planned with 8 participants in each cohort, for a total of 24 participants who receive sufficient doses of the investigational medication to assess safety (Section 4.5).

The doses planned for each ascending dose cohort include 0.6mg/kg, 1.2 mg/kg, and 1.8 mg/kg brentuximab vedotin or placebo equivalent. All cohorts will receive intravenous administration of study medication every 3 weeks for 21 weeks, for a total of eight doses. Following completion of treatment, participants will undergo follow-up visits at weeks 24, 28, 36 and 48.

After completion of the first 12 weeks of treatment for each of the first two cohorts of 8 participants, an interim safety analysis will be conducted and reviewed by an independent Safety Review Committee, as described in Section 8.11.2. Approval by the Safety Review Committee following the 12-week interim safety analysis will be required before proceeding to the next higher dose of brentuximab vedotin.

Interim safety analysis will also be conducted at 24 weeks following completion of study treatment for each of the first two cohorts of 8 participants. Following either the week 12 or the week 24 interim safety reviews, the Safety Review Committee can recommend actions regarding study conduct, as described in Section 8.11.2.

[figure not shown]

Figure 1. Study Schema

3.2 STUDY REGIMEN

Brentuximab vedotin or placebo.

- Cohort 1: Intravenous brentuximab vedotin 0.6 mg/kg or placebo every three weeks for eight doses.
- Cohort 2: Intravenous brentuximab vedotin 1.2 mg/kg or placebo every three weeks for eight doses.
- Cohort 3: Intravenous brentuximab vedotin 1.8 mg/kg or placebo every three weeks for eight doses.

3.3 STUDY DURATION

Total study duration target is 308 weeks:

- Enrollment phase duration target is 260 weeks.
- Study participation phase for each participant is 48 weeks, which includes a treatment phase of 21 weeks and a follow-up phase of 27 weeks.

3.4 STUDY ENDPOINTS

3.4.1 Primary Endpoint

The primary endpoint will be the proportion of participants who experience at least one Grade 3 or higher adverse event at or before week 48.

3.4.2 Secondary Endpoints

Safety Endpoints:

- 1. The proportion of participants who experience at least one Grade 3 or higher adverse event at or before weeks 12, 24 and 36.
- 2. The proportion of participants who experience at least one Grade 2 or higher adverse event at or before weeks 12, 24, 36, and 48.
- 3. The proportion of participants with Grade 2 or higher peripheral neuropathy at or before weeks 12, 24, 36, and 48.
- 4. The proportion of participants with Grade 3 or higher neutropenia at or before weeks 12, 24, 36, and 48.
- 5. The proportion of participants with any of the following Grade 3 or higher adverse events at or before week 48:
 - a. Peripheral neuropathy.
 - b. Neutropenia.
 - c. Infectious adverse events.
 - d. Infusion reactions, including anaphylaxis and new onset rash consistent with Stevens-Johnson syndrome, toxic epidermal necrolysis, or other drug reaction.
 - e. PML.

Exploratory Efficacy Endpoints:

- 1. Modified Rodnan Skin Score (mRSS) at weeks 12, 24, and 48.
- 2. Provisional American College of Rheumatology Combined Response Index in Systemic Sclerosis (CRISS) [75] at weeks 24 and 48.
- 3. Percent predicted Forced Vital Capacity (FVC) at weeks 24 and 48 weeks.
- 4. Physician's global assessment on a Likert scale at weeks 24 and 48.
- 5. Patient's global assessment on a Likert scale at weeks 24 and 48.

- 6. Health-related quality of life (HRQOL) assessed by PROMIS-29 version 2.0 at weeks 24 and 48.
- 7. Physical function assessed by the Scleroderma Health Assessment Questionnaire-Disability Index (SHAQ-DI) at weeks 24 and 48.

3.5 RATIONALE FOR SELECTION OF DRUG, ROUTE, DOSE, AND REGIMEN

The brentuximab vedotin route, dose, and regimen was selected based on the suggested dosing and administration of brentuximab vedotin for relapsed or refractory classical Hodgkin's lymphoma and systemic anaplastic large cell lymphoma [55]. The dose recommended in the prescribing information is 1.8 mg/kg administered intravenously every three weeks for a maximum of 16 doses.

Since the current study is a dose escalation safety evaluation in a non-oncology indication, the first cohort will receive one third of the recommended dose of brentuximab vedotin (0.6 mg/kg) for eight doses, the second cohort will receive two thirds of the recommended dose of brentuximab vedotin (1.2 mg/kg) for eight doses, and the final cohort will receive the recommended oncology dose of brentuximab vedotin (1.8 mg/kg) for eight doses.

Of note, Seattle Genetics undertook a dose escalation study of brentuximab vedotin in SLE [65]. The trial was planned as a blinded randomized safety study in a total of 40 adult participants with active SLE, with each cohort of 10 participants receiving one of four escalating doses of brentuximab vedotin or placebo. The primary outcome measures were the number and percentage of participants experiencing adverse events over a 127-day time frame. Although no safety concerns were noted in the first two dosing cohorts, Seattle Genetics terminated the study before completion due to revised business portfolio prioritization (NCT02533570).

4. ELIGIBILITY

4.1 INCLUSION CRITERIA

Patients must meet *all* of the following criteria to be eligible for this study:

- 1. Classification of systemic sclerosis (SSc), as defined using the 2013 American College of Rheumatology/European Union League Against Rheumatism classification of SSc [76].
- 2. Diagnosis of dcSSc, as defined by LeRoy and Medsger [77].
- 3. Disease duration \leq 60 months (defined as time from the first non-Raynaud phenomenon manifestation).
- 4. mRSS units \geq 15 and \leq 45, and both of the following:
 - a. At least mild skin thickening ($\geq 1+$ mRSS) of the forearm, and

- b. At least moderate skin thickening (≥ 2+ mRSS) at the planned forearm skin biopsy site.
- 5. Documentation of at least 12 weeks of ongoing immunosuppressive therapy for SSc at the time of enrollment, and at least 4 weeks at a stable dose, of one of the following:
 - a. Methotrexate ≤ 25 mg/week, or
 - b. Mycophenolate mofetil ≤ 3 grams/day or mycophenolate sodium ≤ 2.16 grams/day, or
 - c. Azathioprine $\leq 3 \text{mg/kg/day}$.
- 6. Age 18-70 years inclusive.
- 7. Completion of primary SARS-CoV-2 vaccination series is required at least 14 days prior to the first infusion of study medication at Visit 0. The dose and schedule of the vaccine is defined according to current FDA approval or Emergency Use Authorization at the time of screening.
- 8. Ability to provide informed consent.

4.2 EXCLUSION CRITERIA

Patients who meet any of the following criteria will *not* be eligible for this study:

- 1. Rheumatic disease other than dcSSc; it is acceptable to include patients with osteoarthritis, fibromyalgia, sicca symptoms, and scleroderma-associated myopathy.
- 2. Limited cutaneous SSc or sine scleroderma.
- 3. Pulmonary disease with FVC \leq 60% of predicted, or DLCO (corrected for hemoglobin) \leq 60% of predicted.
- 4. Pulmonary hypertension (PH) or moderate to severe left ventricular dysfunction, defined as one of the following:
 - a. Transthoracic echocardiography demonstrating at least one of the following (unless subsequent right heart catheterization does not demonstrate PH; or unless prior right heart catheterization within one year did not demonstrate PH and echocardiography results are not significantly changed):
 - i. Tricuspid regurgitation jet >2.8 m/sec or estimated right ventricular systolic pressure > 42 mm Hg, or
 - ii. At least one of the following:
 - 1. Abnormality of right atrial size, shape, or wall thickness consistent with PH, or
 - 2. Abnormality of right ventricular size, shape, or wall thickness consistent with PH, or
 - 3. Abnormal septal wall shape consistent with PH.
 - iii. Left Ventricular Ejection Fraction (LVEF) < 50%.

- b. Right heart catheterization showing mean pulmonary artery pressure ≥25 mm Hg at rest.
- c. Current use of approved medications for PH. It is acceptable to use phosphodiesterase type 5 (PDE-5) inhibitors for Raynaud's, digital ulcers, and intermittently for erectile dysfunction.
- 5. Active scleroderma renal crisis within the 4 months prior to enrollment.
- 6. History of moderate-to-severe lower gastrointestinal dysmotility such as current use of parenteral nutrition and/or recent history of intestinal pseudo-obstruction within 3 months prior to enrollment.
- 7. The following medications:
 - a. Oral corticosteroids >10 mg/day of prednisone or equivalent within 2 weeks prior to enrollment.
 - b. Treatment with intravenous immunoglobulin (IVIG) within 12 weeks prior to enrollment.
 - c. Treatment with cyclophosphamide within 6 months prior to enrollment.
 - d. Use of investigational biologic or non-biologic medication within the past 90 days, or 5 half-lives prior to enrollment, whichever is greater, except for SARS-CoV-2 vaccines, and medications used for prevention and treatment of COVID-19, per FDA Emergency Use Authorization.
 - e. Use of anti-TNF medication or other biologic medications within the past 90 days, or 5 half-lives prior to enrollment, whichever is greater.
 - f. Prior treatment with anti-CD20 if either of the following are true:
 - i. B cells \leq lower limit of normal (LLN), or
 - ii. Treatment with anti-CD20 has been within 12 months prior to enrollment.
 - g. Any prior treatment with cell-depleting therapies other than anti-CD20, including investigational agents, including but not limited to, CAMPATH®, anti-CD4, anti-CD5, anti-CD3, anti-CD19.
 - h. Any prior treatment with chlorambucil, bone marrow transplantation, or total lymphoid irradiation.
- 8. Receipt of a live-attenuated vaccine within 3 months of study enrollment.
- 9. Concomitant malignancies or a history of malignancy, with the exception of adequately treated basal and squamous cell carcinoma of the skin, or carcinoma in situ of the cervix.
- 10. Major surgery (including joint surgery) within 8 weeks prior to enrollment.
- 11. History of solid organ or hematopoietic stem cell transplantation.
- 12. History of primary immunodeficiency.

- 13. Comorbidities requiring systemic corticosteroid therapy, including those which have required three or more courses of systemic corticosteroids within the 12 months prior to enrollment.
- 14. Current substance abuse or history of substance abuse within 12 months prior to enrollment.
- 15. History of severe depression or severe psychiatric condition.
- 16. Lack of peripheral venous access.
- 17. Known hypersensitivity to brentuximab vedotin, a component thereof, or the excipient contained in the drug formulation.
- 18. Severe, progressive, or uncontrolled renal, hepatic, hematological, gastrointestinal, pulmonary, cardiac, or neurological disease (or, in the investigator's opinion, any other concomitant medical condition that places the participant at risk by participating in this study), including but not limited to:
 - a. Uncompensated congestive heart failure (New York Heart Association Class III or VI).
 - b. Clinically significant active coronary artery disease (e.g., unstable angina or acute myocardial infarction within 6 months prior to enrollment).
 - c. Recently active cerebrovascular disease (e.g., stroke or transient ischemic attack within 6 months prior to enrollment).
 - d. Uncontrolled systemic hypertension.
 - e. Confirmed diagnosis of diabetes mellitus.
 - f. Pancreatitis within 30 days prior to enrollment.
 - g. History or presence of peripheral neuropathy, such as mononeuritis multiplex, acute or chronic inflammatory demyelinating polyneuropathy, axonal sensorimotor neuropathies, or drug related neuropathy or neuritis.
- 19. Evidence of infection:
 - a. Any infected ulcer at enrollment.
 - b. Active bacterial, viral, fungal, or opportunistic infections requiring systemic anti-infective therapy.
 - c. Evidence of current or prior infection with tuberculosis
 - i. Positive QuantiFERON® TB Gold or TB Gold Plus test results. Purified protein derivative (PPD) tuberculin test may be substituted for QuantiFERON® TB Gold or TB Gold Plus test.
 - ii. Indeterminant QuantiFERON® TB Gold or TB Gold Plus test results, unless followed by a subsequent negative PPD or negative QuantiFERON® and clearance by local Infectious Disease department.
 - d. Evidence of current or prior infection with
 - i. Human immunodeficiency virus (HIV), or

- ii. Hepatitis B (as assessed by hepatitis B surface antigen, HBsAg and antibody to hepatitis B core antigen, anti-HBc) or
- iii. Hepatitis C (HCV), except adequately treated HCV with documentation of sustained virologic response defined as undetectable HCV RNA at least 12 weeks after the end of treatment.
- e. History of progressive multifocal leukoencephalopathy (PML).
- f. Hospitalization for treatment of infections, or parenteral (intravenous or intramuscular) antibacterial, antivirals, anti-fungal, or anti-parasitic agents within the past 60 days prior to enrollment.
- g. Chronic infection that is currently being treated with systemic suppressive antibiotic or antiviral therapy, including but not limited to tuberculosis, pneumocystis, cytomegalovirus, herpes simplex virus, herpes zoster, and atypical mycobacteria.
- h. History of significant infection or recurrent infection that, in the investigator's opinion, places the participant at risk by participating in this study.
- i. Positive PCR test for SARS-CoV-2 within 14 days prior to enrollment.
- 20. The following laboratory abnormalities:
 - a. Neutropenia (absolute neutrophil count <1500/mm³).
 - b. Thrombocytopenia (platelets <100,000/mm³).
 - c. Moderately severe anemia (hemoglobin < 10 g/dL).
 - d. Liver function test (aspartate aminotransferase [AST], alanine aminotransferase [ALT], or alkaline phosphatase) results that are ≥ 1.5 times the upper limit of normal.
 - e. Serum total bilirubin > 1.5 times the upper limit of normal, or > 3 times the upper limit of normal in the presence of Gilbert's syndrome.
 - f. Serum amylase and serum lipase > 1.5 times the upper limit of normal.
- 21. Renal dysfunction, defined as either one of the following:
 - a. Serum creatinine > 1.5 times the upper limit of normal.
 - b. Estimated glomerular filtration rate (eGFR) \leq 60 mL/min/1.73m².
- 22. Pregnancy.
- 23. Breastfeeding.
- 24. Unwillingness to use two forms of medically acceptable contraception methods by participants and their partners (if of reproductive potential) during the study and for at least 6 months after last dose of study drug.
- 25. Inability to comply with study and follow-up procedures.

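### Exclusion 4 names left ventricular dysfunction, but its only LVEF criterion is waived when catheterization shows no pulmonary hypertension

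*Protocol*

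**What the plan says.** Item 4 of Protocol Section 4.2 opens with two conditions and a single list of definitions: "Pulmonary hypertension (PH) or moderate to severe left ventricular dysfunction, defined as one of the following". The list has three entries.

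- **4.a** is echocardiographic. Its stem holds a waiver with two limbs. The first reads "Transthoracic echocardiography demonstrating at least one of the following (unless subsequent right heart catheterization does not demonstrate PH". The second reads "or unless prior right heart catheterization within one year did not demonstrate PH and echocardiography results are not significantly changed". Three sub-items follow: (i) a tricuspid jet velocity or an estimated right ventricular pressure above a limit; (ii) right atrial, right ventricular or septal abnormalities, each qualified as consistent with PH; and "iii. Left Ventricular Ejection Fraction (LVEF) < 50" per cent.
- **4.b** is "Right heart catheterization showing mean pulmonary artery pressure ≥25 mm Hg at rest".
- **4.c** is "Current use of approved medications for PH", with an allowance for PDE-5 inhibitors in other uses.

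The Exclusion Criteria in the synopsis carry the same waiver wording and the same order, with the LVEF line after the PH signs and before 4.b.

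**The concern.** The waiver answers one question, whether a suggestive echocardiogram really reflects PH. It is sensible for sub-items i and ii, which are indirect signs of PH that catheterization can refute. Sub-item iii is a measurement of left ventricular function, and a catheterization that rules out PH does not address it. Because iii sits under the same stem, the one criterion that gives effect to the left ventricular half of the heading is removed by a finding about the other half.

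A site that follows the text exactly could therefore pass, under item 4, a person whom the heading says is excluded. Another site that follows the heading would exclude the same person. In a first safety study in this disease, with 8 participants per cohort, the eligibility rule should have one reading.

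**Working it through.** No sample size, error rate or event count bears on this point, so the check is one of logic.

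**Inputs (Protocol Section 4.2, item 4).** Let P be any sign in 4.a.i or 4.a.ii; L be LVEF below 50% (4.a.iii); W1 be a later catheterization without PH; W2 be a catheterization within one year without PH and an echocardiogram not significantly changed; B be 4.b; C be 4.c.

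**Rule as written.** The waiver stands in the stem, before sub-item i, so it governs all three sub-items:

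Excluded by item 4 = [(P or L) and not (W1 or W2)] or B or C.

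**Rule if LVEF is listed separately.**

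Excluded by item 4 = [P and not (W1 or W2)] or L or B or C.

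**Cases, all with LVEF below 50% and no PH medication (L true, C false).** A catheterization that does not demonstrate PH is taken to mean that 4.b is false.

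| Case | W1 or W2 | B | As written | LVEF listed separately |
|---|---|---|---|---|
| No catheterization | false | false | excluded | excluded |
| Catheterization shows mean pressure at or above the 4.b limit | false | true | excluded | excluded |
| Later catheterization without PH | true (W1) | false | **not excluded** | excluded |
| Catheterization within one year without PH, echocardiogram unchanged | true (W2) | false | **not excluded** | excluded |

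Once the waiver is met, the rule as written reduces to B or C, and both are about PH. LVEF no longer affects the result. Under the second limb, an LVEF that is low but stable helps to satisfy the condition that the echocardiogram has not changed.

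**Does another criterion close the gap?** Item 18 excludes cardiac disease that is severe, worsening or poorly controlled, and any condition that the investigator considers a risk. Sub-item 18.a covers uncompensated heart failure. Neither gives an LVEF value, and no other exclusion does. A stable, compensated participant with LVEF below 50% may or may not be excluded under item 18, depending on judgement.

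**Signs of a drafting slip.** Sub-item i ends with a connecting word, but the last part of ii ends in a full stop with nothing linking it to iii. Every part of ii refers to PH and iii does not. This fits an item appended to a PH list, but it is an inference; the protocol does not say so.

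**The case against.** The strongest reply is that passing item 4 is not the same as being eligible. A reader might infer that a low LVEF plus a clean catheterization admits the participant. The documents do not support that: the stem of item 18 is broad, its list is expressly not exhaustive, and it gives the investigator a written ground to exclude. This stands, and it limits the claim to item 4. It does not remove the defect, because item 18 replaces a stated threshold with judgement.

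The route is also narrow. Catheterization is not a study procedure: Section 6.5 and Appendix 1 list only the EKG and echocardiogram, and Section 6.1.1 allows at most 28 days between Visit -1 and Visit 0. The waiver depends on a catheterization obtained outside the study schedule. This stands too.

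Three further inferences are tempting and should not be drawn.

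- One could measure the harm by the move from 0/6 to 1/6 in Table 3. Any Grade 3 or higher event in any active participant does that, so it does not measure this defect; it also assumes assignment to active drug, when 2 of 8 per cohort receive placebo.
- One could say that a cardiac event in such a participant could not be told apart from drug toxicity. Section 8.3.3 requires an attribution for each event, Section 9.2.6 reports relationship to study drug, and Section 9.2.3 merges the cohorts, which brings together the planned 3 × 2 = 6 placebo participants.
- One could take the wording of 18.a, "Uncompensated congestive heart failure (New York Heart Association Class III or VI", as proof that the backstop fails. The class number is an evident typing error inside a non-exhaustive list, and uncompensated failure is excluded by the words before it.

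Finally, the numbering of the LVEF line in the synopsis cannot be read in the text available, so only its wording and order can be confirmed there, not its level in the list.

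**Conclusion.** The point holds in a limited form. As written in Section 4.2, the left ventricular criterion of exclusion 4 is lifted by a finding that concerns only PH, which contradicts the heading of the item. A participant with LVEF below 50%, a catheterization without PH and no PH medication is not excluded by item 4.

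The practical size is small. The protocol gives no frequency of reduced LVEF or of catheterization among candidates, so no count can be derived, and some of those concerned would be stopped under item 18. No sample size, interval or probability in Section 9 is affected. The conclusion rests on the literal position of the waiver in the stem of 4.a and on reading a catheterization without PH as one that does not meet 4.b. It does not claim that such participants are eligible overall, nor does it say what LVEF rule is clinically right. It is worth correcting because the rule bears on safety and the text can be followed in two ways.

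**What to change.** Reconcile the heading, the waiver and sub-item iii of exclusion 4, in Section 4.2 and in the synopsis, and state whether the waiver is meant to reach the LVEF item.

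- The edit consistent with the present heading is to move "Left Ventricular Ejection Fraction (LVEF) < 50" per cent out of 4.a and list it as its own entry, so that the waiver applies only to the PH signs in 4.a.i and 4.a.ii.
- If the sponsor does intend a catheterization without PH to lift the LVEF item, the heading should be reworded to say so.

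The cost is the rewording of one criterion in two places. No test is added, because Appendix 1 already has the echocardiogram at Visit -1. If LVEF is listed separately, the downside is that the very few candidates who would have used the waiver are excluded.

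As a separate editorial matter, correct the NYHA class in 18.a, which reads the same in Section 4.2 and in the synopsis.
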